2.2 Analysis sets

For all analysis sets, participants will be analyzed according to the study treatment(s) received.

The safety analysis set will include all participants who received any study drug.

The PK analysis set will include all participants with at least one available valid (i.e., not flagged for exclusion) PK concentration measurement, who received any study drug and with no protocol deviations that impact PK data. Participants in the placebo arm will be excluded from PK analysis set.

The PD analysis set will include all participants with available PD data and no protocol deviations with relevant impact on PD data.

The analysis sets and protocol deviation codes are related as Table 2-1.

Table 2-1 Protocol deviation codes and analysis sets

Category Deviation code	Text description of deviation	Data exclusion
Subjects are excluded from S	Safety analysis in case of these PDs:	Exclude subject from Safety analysis set
WITH01	Subject withdrew consent but continue to receive study medication	Υ
Subjects are excluded from F	PK analysis in case of these PDs:	Exclude subject from PK analysis set
WITH01	Subject withdrew consent but continue to receive study medication	Y
CCI	CCI	Y
Subjects are excluded from F	PD analysis in case of these PDs:	Exclude subject from PD analysis sets
WITH01	Subject withdrew consent but continue to receive study medication	Υ
INCL04	Absence of history of PAH subgroups of clinical classification group 1 as defined in Protocol	Y
INCL05A	Resting mPAP is <25 mmHg, PCWP or left ventricular end diastolic pressure >15 mmHg as determined by RHC	Y
INCL06A		Pulmonary Vascular Resistance is <6 WU corresponding to 480 dynes s/cm5 as determined by RHC
INCL07	Patient doesn't have PAH of WHO Functional Class II – III	Υ
EXCL03	Patients with PH in clinical classification groups 2-5 (WHO) and any PAH group 1 subgroups not covered by IE 4	Y
CCI	CCI	Y

Protocol deviations mentioned above, and analysis sets will be reviewed in the data review meeting to decide inclusion or exclusion of participant(s) from analyses sets. Decisions regarding the exclusion of participants and/or participant data from analyses will be made prior to final database lock (DBL).

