### 9.2 Withdrawal of informed consent/Opposition to use data/biological samples

Withdrawal of consent/opposition to use data/biological samples occurs when a participant:

Explicitly requests to stop use of their biological samples and/or data (opposition to use participant's data and biological samples)

and

No longer wishes to receive study treatment

and

Does not want any further visits or assessments (including further study-related contacts)

This request should be as per local regulations (e.g. in writing) and recorded in the source documentation.

Withdrawal of consent impacts ability to further contact the participant, collect follow-up data (e.g. to respond to data queries) and potentially other country-specific restrictions. It is therefore very important to ensure accurate recording of withdrawal vs. discontinuation based on the protocol definitions of these terms.

In this situation, the investigator should make a reasonable effort (e.g. telephone, e-mail, letter) to understand the primary reason for the participant's decision to withdraw their consent/ exercise data privacy rights and record this information. The Investigator shall clearly document if the participant has withdrawn his/her consent for the use of data in addition to a study discontinuation.

Study treatment must be discontinued and no further assessments conducted, and the data that would have been collected at subsequent visits will be considered missing.

Further attempts to contact the participant are not allowed unless safety findings require communicating or follow-up.

If the participant agrees, a final evaluation at the time of the participant's withdrawal of consent/opposition to use data/biological samples should be made as detailed in the assessment table (refer to Section 8).

Further details on withdrawal of consent or the exercise of participants' data privacy rights are included in the corresponding informed consent form.

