2.3 Patient disposition, demographics and other baseline characteristics

2.3.1 Patient disposition

A summary table will be presented including the number and percentage of participants

- Who were randomized to treatment groups and overall
- Who completed the study
- Who discontinued from study (overall and by the primary reason for discontinuation)

The number and percentage of participants in each analysis set will be tabulated by treatment group. The percentage will be based on all randomized participants.

A listing of all participants excluded from any analysis sets will be provided with reasons for exclusion (i.e., including both protocol and non-protocol deviations)

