2.7 Safety analyses

For all safety analyses, the safety set will be used. All listings will be presented by treatment group, and tables will be presented by treatment group and overall. Safety summaries (tables, figures) include only data from the on-treatment period except for baseline data which will also be summarized where appropriate (e.g. change from baseline summaries).

The on-treatment period lasts from the date of first administration of study treatment to the EOS visit (about 30 days after the date of the last actual administration of any study treatment).

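### SAP Table 2-1 by default drops from the safety set anyone who withdrew consent but kept taking study drug, against the set's own definition, and keys the rule to dosing instead of opposition to data use

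*SAP*

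**What the plan says.** SAP 2.2 defines the set without qualification: "The safety analysis set will include all participants who received any study drug". Protocol 12.1 gives the same definition and attaches no deviation-based exclusion to it.

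Table 2-1 in the same SAP section links deviation codes to analysis sets. Its only visible safety-set code is WITH01, described as "Subject withdrew consent but continue to receive study medication", and the column that applies reads "Exclude subject from Safety analysis set". The same code is listed for the PK and PD sets.

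Three other statements matter:

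- SAP 2.7: "For all safety analyses, the safety set will be used".
- The text below Table 2-1 sends the listed deviations and the analysis sets to a data review meeting. That meeting decides who is included or excluded before final database lock, and it may act on participants or on parts of their data.
- SAP 2.3.1: "A listing of all participants excluded from any analysis sets will be provided with reasons for exclusion".

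Protocol 9.2 describes withdrawal of consent as including an explicit request to stop use of samples and/or data. It requires study treatment to be discontinued and no further assessments to be made, and adds that "the data that would have been collected at subsequent visits will be considered missing". SAP 4 states that the analysis does not depart from the protocol.

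**The concern.** A safety set exists to count everyone exposed. A rule that removes a participant known to have been exposed, for a reason other than non-exposure, defeats that purpose. Here the removal is of the whole subject with no cut at the withdrawal date, so events recorded while consent was in force go too.

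The trigger is also hard to justify. If the aim is to respect a participant's wish that data not be used, the rule should follow that wish. As written, continued dosing decides the matter. Someone who withdraws and stops dosing meets no visible safety-set exclusion, while someone who withdraws and goes on dosing, and so has more exposure, is taken out.

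Protocol 4.5 describes LTP001 as the first SMURF1 inhibitor in development, with no known class effects to draw on. In a study of about 44 people, single events in the safety tables will be read closely.

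**Working it through.** The plan gives no figure to reproduce for this point. The check is a comparison of passages, followed by simple proportions to show scale.

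1. **Definition against exclusion row.** Membership requires only receipt of study drug (SAP 2.2, Protocol 12.1). WITH01 presupposes receipt of study drug both before and after withdrawal. Every WITH01 case therefore meets the definition, and Table 2-1 excludes every WITH01 case. The two rules cannot both be applied.

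2. **Unit of exclusion.** The column heading refers to the subject, and no date limit is given. Because SAP 2.7 runs all safety analyses on the safety set, exclusion from the set removes the person's adverse event, laboratory, ECG and vital sign data from the summaries, and removes the person from the denominator.

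3. **Trigger.** Compare two participants who both withdraw consent:
   - A stops dosing: no visible safety-set code applies, so A stays in.
   - B continues dosing: WITH01 applies, so B is out by default.

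   Withdrawal as Protocol 9.2 defines it is common to both. Only dosing separates them. Protocol 9.2 already asks the investigator to record clearly whether consent to data use has been withdrawn, so the relevant fact is available as a trigger.

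4. **Declared changes.** SAP 4 reports none, although Protocol 12.1 has no such exclusion. The SAP cites protocol version 02 and the protocol at hand is version 03, but the stated rationale for Amendment 03 mentions no change to the analysis sets.

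5. **Other sets.** The PK and PD definitions already exclude participants whose deviations affect the data concerned. WITH01 in those rows does not contradict the set definition.

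6. **Scale.** Inputs: about 44 randomized, 3:1 (SAP 3), assuming all are treated.
   - LTP001: 44 × 3/4 = 33. Placebo: 44 × 1/4 = 11.
   - One excluded participant who had the only event of its type: LTP001 goes from 1/33 = 3.0% to 0/32 = 0%; placebo goes from 1/11 = 9.1% to 0/10 = 0%.
   - One excluded participant without that event, another LTP001 participant having it: 1/33 = 3.0% becomes 1/32 = 3.1%.

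   The denominator shift is trivial. What matters is the possible loss of a rare event.

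**The case against.** The strongest reply is that Table 2-1 is only a default. The data review meeting can keep the participant or limit the exclusion to some data, and anyone excluded is listed with a reason. This stands: removal is not automatic, and a reader who infers that all earlier adverse events must vanish from every output goes too far. It does not cure the conflict. The SAP gives no criterion for overriding the table, and the exclusion listing is not said to show adverse events. SAP 2.13 also has the clinical team reviewing unblinded interim results, and SAP 2.2 does not say that those deciding exclusions are blinded. That is no evidence of biased decisions, but it favours a fixed rule.

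The second reply is that withdrawal, in Protocol 9.2 and the glossary, includes a request to stop data use, so removal may be what the participant asked for. This also stands in part. It is tempting to read Protocol 9.2 as making only post-withdrawal data unavailable, but the sentence quoted above concerns visits that no longer take place. It does not settle what happens to data already collected. Any repair must therefore leave room for a documented objection. What the reply cannot explain is a rule that depends on whether dosing continued.

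Several stronger inferences should be set aside:

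- A death before withdrawal cannot be lost this way, because that person could not later withdraw and go on dosing.
- Informative loss through poor tolerability is a weak argument here, since those who withdraw for intolerance would be expected to stop the drug.
- SAE reporting to the sponsor within 24 hours (Protocol 10.1.3) does not depend on analysis-set membership.
- A material effect on the primary analysis is not supported. WITH01 also removes the participant from the PD set, but someone who withdraws before Week 25 would normally have no Week 25 PVR, and SAP 2.5.4 does not impute it.

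**Conclusion.** The contradiction is real and rests on the text alone: the safety-set definition and the WITH01 row cannot both hold, and the row's trigger does not match the only reason the documents suggest for removing data. The consequence is conditional on a WITH01 case occurring and on the data review meeting leaving the default in place.

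The expected number of cases is small but not given. A case needs a breach of Protocol 9.2, which requires treatment to stop at withdrawal. Per case, the loss is one of about 33 (3.0%) on LTP001 or one of about 11 (9.1%) on placebo, assuming the planned split and that all randomized participants are treated. It affects the planned safety summaries, not safety reporting during the trial. The reading that no other safety-set code exists is limited to the visible rows of Table 2-1.

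This is an inexpensive correction to a rule that is wrong as written. It does not threaten the trial's conclusions.

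**What to change.** - Delete the WITH01 row for the safety set in SAP Table 2-1, so that the table agrees with SAP 2.2 and Protocol 12.1.
- Add a data-level rule: the participant stays in the safety set with data collected up to the date of consent withdrawal, and data collected after that date are excluded.
- Remove earlier data only where the participant's documented opposition to data use under Protocol 9.2 requires it, whether or not dosing continued. Footnote the number removed, by arm.
- Optionally apply the same rule to the WITH01 rows for PK and PD. This is for consistency only, as those rows do not conflict with their definitions.

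The cost is one deleted row and a short paragraph in SAP 2.2, a date cut in the safety programming, and a table footnote; editing PK and PD as well touches two more rows. It needs no new data collection, because Protocol 9.2 already asks for the data-use decision to be documented. It should be done before database lock.

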2.2.1 Subgroup of interest

Not applicable.

2.3 Patient disposition, demographics and other baseline characteristics

2.3.1 Patient disposition

A summary table will be presented including the number and percentage of participants

- Who were randomized to treatment groups and overall
- Who completed the study
- Who discontinued from study (overall and by the primary reason for discontinuation)

The number and percentage of participants in each analysis set will be tabulated by treatment group. The percentage will be based on all randomized participants.

A listing of all participants excluded from any analysis sets will be provided with reasons for exclusion (i.e., including both protocol and non-protocol deviations)

2.3.2 Demographics and other baseline characteristics

Demographics and other baseline data including disease characteristics will be summarized descriptively by treatment group and overall utilizing the safety set. Categorical data will be presented as frequencies and percentages. For continuous data, mean, standard deviation, median, minimum, and maximum will be presented. For selected parameters, 25th and 75th percentiles will also be presented.

Participant demographics will include age, gender, race, ethnicity & BMI.

The following clinical baseline characteristics will be summarized separately:

- Time since PAH diagnosis
- PAH classification
- Standard of care
- Smoking history
- WHO functional Class
- 6 Minute Walk Test and Borg Scale
- PVR
- Echocardiography parameters
- Lung function test
- NT-proBNP
- Concomitant PAH medication (classified as per the inclusion criteria; prostacyclin analogues and receptor agonists
- endothelin receptor antagonists
- phosphodiesterase type 5 inhibitors

[figure not shown]
soluble guanylate cyclase stimulators)

Relevant medical history and current medical conditions at the baseline will be listed by the treatment group and participant.

2.4 Treatments (study treatment, rescue medication, concomitant therapies, compliance)

The Safety set will be used for treatment related summaries. Categorical data will be summarized as frequencies and percentages. For continuous data, N, mean, standard deviation, median, 25th and 75th percentiles, minimum, and maximum will be presented.

2.4.1 Study treatment / compliance

The treatment period is for 24 weeks with participants' visits at week 1, week 5, week 9, week 13, week 17, week 21, week 25. Participants are instructed to take the study treatment exactly as prescribed and to contact the investigator if he/she is unable for any reason to take the study treatment as prescribed.

Compliance will be assessed by the investigator and/or study personnel at each visit using pill counts and information provided by the participant. The information will be captured in the source document at each visit. All study treatment dispensed and returned will be recorded in the Drug Accountability Log. Off-site treatment compliance will be assessed by the OHP and details of which will be shared with the investigator.

Participants will be instructed not to make up missed doses. A missed dose is defined as a case when the full dose is not taken within 12 hours after the approximate time of the usual daily dosing. That day's dose should be omitted, and the participant should continue treatment with the next scheduled dose.

Pill counts (including counts of dispensed/returned pills) will be listed by participants, and visits, with relevant information about compliance provided by the participant if data is available.

2.4.2 Prior, concomitant and post therapies

Concomitant medications and significant non-drug therapies prior to and after the start of the study treatment for participants in the safety set will be listed according to the Anatomical Therapeutic Chemical (ATC) classification system, by treatment group.

2.5 Analysis supporting primary objective(s)

2.5.1 Primary endpoint(s)

To assess the efficacy of LTP001 in participants with pulmonary arterial hypertension (PAH), the primary endpoint of the study will be the change from baseline in Pulmonary Vascular Resistance (PVR) at Week 25. PVR is defined as the resistance against blood flow from the pulmonary artery to the left atrium measured in dyn·s·cm-5.

2.5.3 Handling of intercurrent events

Not applicable.

2.5.4 Handling of missing values not related to intercurrent event

Missing data will not be imputed.

2.5.5 Sensitivity analyses

The primary analysis will be repeated assuming a non-informative prior for placebo treatment group. This would allow us to capture the results without using any historical control data.

Due to the fact that the WHO functional classification tents to be sparse, a model without WHO functional classification will be fitted.

In the event of protocol deviations relevant for inclusion criteria or documented as any deviations from the standardized procedures for PVR collection, the primary analysis will be repeated excluding these subjects.

An analysis of covariance (ANCOVA) will be conducted with treatment as fixed effect and baseline as covariate to support the result of the primary analysis.

An analysis of residuals will be carried-out to assess model assumption. If the underlying normality assumption for analysis of covariance (ANCOVA) is not met, then alternative methods will be considered such as Hodges—Lehmann (Lehmann & Hodges, 1963) or log-transformed data.

2.5.6 Supplementary analyses

Not applicable.

2.6 Analysis supporting secondary objectives

All analysis of secondary endpoints will be performed on the PD analysis set. Missing data for any reason will not be explicitly imputed and will be handled by the respective mixed effects model (if performed) which implicitly imputes missing data assuming missing at random (MAR).

2.6.1 Secondary endpoint(s)

Six Minute Walk Test

This measures how many meters a person can walk in 6 minutes. It includes total distance walked (6MWD), the number and duration of any stops in 6 minutes. Test performed at baseline and at visits on Week 13, and 25 will be used for analysis.

Right Heart Catheterization (RHC)

The RHC is performed to assess several hemodynamic parameters when the patient is in a stable hemodynamic rest state (as demonstrated by three consecutive cardiac output measurements with 10% of each other). The measurement is taken at baseline and at visit on Week 25. The assessed hemodynamic parameters include:

- right atrial (RA) pressure
- mean pulmonary artery pressure (mPAP)
- pulmonary capillary wedge pressure (PCWP)
- systolic and diastolic blood pressure (RV pressures)

- heart rate (HR)
- cardiac output (CO)
- systemic vascular resistance (SVR)
- mixed venous blood gas measurement

Echocardiography

The echocardiography is performed to assess the impact of study drug on right heart structure and function. All echocardiography images will be centrally read by an imaging vendor. The measurement is taken at baseline and at visit on Week 5, 13, and 25.

The assessed echocardiography parameters include:

- Tricuspid annular plane systolic excursion (TAPSE)
- Tricuspid annular systolic velocity (TASV)
- Peak velocity of excursion (RV S')
- Fractional area change (FAC)

Patient Reported Outcomes (PROs)

The two patient reported outcomes utilized in this study are emPHasis-10 and in PAH-SYMPACT. Change from baseline on Week 13, and 25 will be descriptively summarized.

- The emPHasis-10 questionnaire (Yorke, et al., 2014) consists of 10 items that address breathlessness, fatigue, control and confidence. Each item is scored on a semantic differential six-point scale (0-5) and carries the same weight. Hence, a total emPHasis-10 score is derived simply aggregating scores of the 10 items. It ranges from 0 to 50, with higher scores representing a higher symptom burden.
- The PAH-SYMPACT questionnaire (Mccollister, et al., 2016) (Chin, et al., 2018) consists of 11 symptom items across two domains (cardiopulmonary and cardiovascular symptoms) and 11 impact items across two domains (physical and cognitive/emotional impacts). Symptom items and one item about the use of oxygen are assessed daily for one week; impact items are assessed on the last day of the week. Each item is scored on a five-point scale (0-4) except for the item of using oxygen (scale 0-1). The total PAH-SYMPACT score will be calculated as the sum of impact item scores and mean weekly symptom item scores. For each symptom item, its mean weekly score will be calculated as the average daily item score taken within the 7-day interval.

NT-proBNP

The N-terminal fragment of the prohormone B-type natriuetic peptide (NT-ProBNP) is reflective of right ventricular distress. Measurements collected at baseline and at visits on Week 13, and 25 will be used for analysis.

Time to clinical worsening (TTCW)

TTCW will be defined as time to any of the following events:

Death

- Hospital stay (≥ 24 h) due to worsening of PAH.
- Worsening of PAH resulting in need for lung transplantation or balloon atrial septostomy
- Initiation of parenteral prostanoid therapy, chronic oxygen therapy, or any other PAHspecific therapies or need for increase of diuretics for more than 4 weeks due to worsening of PAH
- Significant drop in 6MWD (15% from baseline or more) due to PAH-worsening

2.6.2 Statistical hypothesis, model, and method of analysis

6MWT

Change from baseline in walked distance for 6MWT at visits will be analyzed based on mixed model repeated measures, adjusting for effects of treatment, visit as categorical factors and treatment*visit and baseline*visit interactions. Model based estimates of the mean effect will be reported for each treatment group along with the treatment difference, the 2-sided 80% confidence interval for treatment difference, and one-sided p-value

TTCW

Time to clinical worsening will be analyzed using survival models (i.e., Kaplan-Meier, cox regression) if adequate number of events occur during the study to characterize the survival curve. Participants without the event will be considered as censored at the end of the time at risk. The hazard ratio and the corresponding 80% confidence intervals will be computed using the appropriate method. If there is no adequate number of events, the number (and percentage) of participants with clinical worsening will be summarized by treatment and overall.

Echocardiography

Descriptive statistics (N, mean, SD, CV% mean, geometric mean, CV% geometric mean, median, min, and max) summarizing echocardiography parameters and their changes from baseline will be summarized by visit for treatment group and overall.

Panels of individual spaghetti plots over time/visit for each echocardiography parameter will be provided.

All echocardiography parameters will be listed by participant, and visit and if ranges are available, abnormalities will be flagged.

PROs

For emPHasis-10, total score and change from baseline of total score will be summarized by visit for treatment and overall. For PAH-SYMPACT, the total score and change from baseline will be summarized by visit for treatment and overall.

NT-proBNP

NT-proBNP (visits on week 13 and 25) will be analyzed based on mixed model repeated measures, adjusting for the baseline, treatment groups, visit and treatment-by-visit interaction. Model based estimates of the mean effect will be reported for each treatment group along with

the treatment difference, the 2-sided 80% confidence interval for treatment difference, and onesided p-value. Depending on the distribution of NT-proBNP data, the analysis for NT-proBNP might be through logarithms to reduce outliers and skewness.

RHC

RHC parameters and their change from baseline will be summarized by visit for treatment group and overall.

Echocardiography parameters, PROs, and RHC are all continuous variables. Summary statistics (including N, mean, SD, minimum, median, and maximum) of each parameter, and graphical presentations (e.g., boxplots) will be provided by visit/time for treatment group, and overall

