2.13 Interim analysis

An unblinded interim analysis (IA) will be carried-out when approximately 20 participants complete the treatment period (Week 25).

This IA will be performed primarily to assess futility (non-binding) on PVR endpoint. The study may be stopped for futility if the posterior probability of the treatment effect no better than placebo is above 60%. Also, analysis for secondary efficacy endpoints, including right heart catheterization results, PROs, NT-proBNP, 6MWD, and TTCW will be performed as described in Section 2.6.

Safety parameters including clinical safety laboratory, ECG, vital signs, and adverse events will be listed and descriptively summarized by treatment and visit/time, if appropriate. More detailed description of the analyses as described in Section 2.7 will be conducted. The study will be stopped if there are three or more (in different participants) similar study-treatment (LTP001) related SAEs that are not related to worsening of PAH (i.e., lack of efficacy by LTP001)

Additional interim analyses may be conducted to support decision making concerning the current clinical study, the sponsor's clinical development projects in general or in case of any safety concerns. Unblinded interim analysis results will be reviewed by the clinical team.

3 Sample size calculation

Approximately 44 participants including dropouts are planned to be randomized in a 3:1 ratio to receive LTP001 vs. placebo on top of SoC. dropout rate is considered to be around 10%.

The sample size calculation was based on the primary endpoint of change from baseline in PVR at Week 25. The criterion for this calculation is based on dual criteria:

- 1. An average change from baseline for PVR over placebo is 100dyn·s·cm⁻⁵ and
- 2. 90% level of proof that the change from baseline for PVR in the LTP001 group is better than placebo.

With a non-informative prior for the LTP001 group, and the obtained weakly informative prior for the placebo group, a sample size of 40 (3:1 ratio of LTP001: placebo) provides approximately 84% chance (power) of meeting the success criterion if the true treatment effect over placebo is 200 dyn·s·cm⁻⁵.

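### NT-proBNP is modelled with one baseline slope for Weeks 13 and 25, unlike 6MWD and without explanation; if the slope changes between visits, a chance baseline imbalance is imperfectly adjusted at Week 25

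*SAP*

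**What the plan says.** SAP 2.6.2 names the method for this marker: "NT-proBNP (visits on week 13 and 25) will be analyzed based on mixed model repeated measures". Its model terms are then listed as "adjusting for the baseline, treatment groups, visit and treatment-by-visit interaction". That list has no baseline-by-visit term, so one baseline coefficient serves both visits.

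The 6MWT paragraph of the same section specifies its model as "adjusting for effects of treatment, visit as categorical factors and treatment*visit and baseline*visit interactions", which gives each visit its own baseline slope.

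The two models otherwise match. SAP 2.6 and 2.6.1 put both on the PD analysis set at Weeks 13 and 25. Both report "the 2-sided 80% confidence interval for treatment difference" and a one-sided p-value.

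The NT-proBNP scale is left open: "the analysis for NT-proBNP might be through logarithms to reduce outliers and skewness". The SAP does not say whether baseline would be logged as well.

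No reason is given for the different baseline term. SAP 2.6.5 offers sensitivity analyses for 6MWT only, and 2.6.6 has no supplementary analyses. Protocol 12.5.1 names the baseline-by-visit term for 6MWT and plans only change-from-baseline summaries for NT-proBNP. Neither document gives an NT-proBNP standard deviation, correlation or baseline slope.

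**The concern.** A single slope is right if NT-proBNP depends on its baseline equally at Weeks 13 and 25. If that dependence changes, the fitted slope is a compromise weighted towards the visit with the smaller residual variance. The Week 25 contrast then carries an error equal to the slope error times the baseline difference between arms.

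A baseline difference is plausible. The sample size rests on 40 analysable participants at 3:1 (SAP Section 3), so about 30 against 10, and the randomisation section of the protocol (6.4.2) names no stratification factor. SAP 2.13 also runs the NT-proBNP analysis at the unblinded interim with about 20 participants. There, at 15:5, one standard error of imbalance is √(1/15 + 1/5) = 0.516 baseline SD.

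At stake is how far the Week 25 NT-proBNP estimate and its p-value move with the baseline imbalance that happens to occur in this one trial.

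**Working it through.** The plan gives no NT-proBNP figure to reproduce, so the check is a formula, a range of assumed inputs, and simulation.

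**From the documents:** the model terms and visits (SAP 2.6.2); 40 participants at 3:1, hence 30:10 (SAP Section 3).

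**Assumed:** log scale with SD 1.1 at every visit, so each slope equals the correlation with baseline; three pairs of Week 13/Week 25 correlations; residual correlation r between the visits of 0.5 to 0.7; unstructured residual covariance; complete data. Using change from baseline as the response alters nothing, since it lowers both slopes by 1.

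**Formula.** With slopes b13 and b25, residual SDs s13 and s25, and cov = r·s13·s25:

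- w = (s25² − cov) / (s13² + s25² − 2·cov)
- b_common = w·b13 + (1 − w)·b25
- Week 25 error = (b25 − b_common) × baseline difference between arms

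**Size of a chance imbalance.** One SE at 30:10 is √(1/30 + 1/10) = 0.365 baseline SD, or 0.365 × 1.1 = 0.402 log units.

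**Worked case, correlations 0.85/0.70, r = 0.7** (in SD units):

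- s13 = √(1 − 0.85²) = 0.527; s25 = √(1 − 0.70²) = 0.714
- cov = 0.7 × 0.527 × 0.714 = 0.263
- w = (0.510 − 0.263) / (0.2775 + 0.510 − 0.527) = 0.946
- b_common = 0.946 × 0.85 + 0.054 × 0.70 = 0.842
- slope error = 0.70 − 0.842 = −0.142
- shift = −0.142 × 0.402 = −0.057 log, about 6% in the ratio (e^0.057 = 1.059)
- SE of the Week 25 difference = 0.714 × 1.1 × 0.365 = 0.287, so the shift is 0.057 / 0.287 = 0.20 SE

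**Range, r = 0.5 to 0.7, one-SE imbalance.** The variance column comes from 20,000 simulated trials per setting (common slope against visit-specific slopes).

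| Correlations, Week 13/25 | Slope error | Shift, log | Shift in ratio | Shift / SE | Extra variance, common slope |
|---|---|---|---|---|---|
| 0.85/0.70 | −0.12 to −0.14 | 0.047 to 0.057 | 5 to 6% | 0.16 to 0.20 | 2 to 3% |
| 0.80/0.60 | −0.15 to −0.19 | 0.062 to 0.075 | 6 to 8% | 0.19 to 0.23 | 2 to 5% |
| 0.90/0.60 | −0.29 to −0.35 | 0.117 to 0.140 | 12 to 15% | 0.36 to 0.43 | 11 to 17% |
| 0.70/0.70 | 0 | 0 | 0 | 0 | none |

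With visit-specific slopes, the simulated Week 25 estimate had essentially no dependence on the imbalance.

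**Operating characteristics.** A second set of simulations (20,000 trials each) fixed the slopes and residual SDs directly: slopes 0.8/0.8, 0.8/0.6 and 0.9/0.5, residual SDs 0.5 to 0.8, residual correlation 0.6 to 0.7.

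- Over all randomisations, the common-slope model had bias of at most 0.003 SD, 80% interval coverage of 0.797 to 0.802, and one-sided 10% error of 0.098 to 0.102.
- Given an imbalance above one SE, its coverage was 0.798 (0.8/0.8), 0.776 to 0.786 (0.8/0.6) and 0.731 (0.9/0.5). With visit-specific slopes it was 0.798 to 0.803.
- With equal slopes, the empirical SD was 0.2223 with visit-specific slopes and 0.2217 with the common slope. The variance cost is (0.2223/0.2217)² − 1, about 0.5%.

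**The case against.** The strongest reply is that nothing has been shown to be wrong. Baseline as a main effect is a legitimate prespecified choice, different endpoints may have different models, and the 6MWD term is carried over from protocol 12.5.1, which requires no such term for NT-proBNP. The two paragraphs do not contradict each other. That stands; what remains is an unexplained difference between otherwise matching models.

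A reader might infer that the Week 25 estimate is wrongly adjusted. The documents do not support this. It needs both a change in slope and a baseline difference between arms, and they give no information on the slopes. Even the direction of the error rests on the assumption that the relation to baseline weakens over time.

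A reader might also infer that the common slope only loses precision. It does not: with equal slopes it is marginally more precise, and in the moderate settings its penalty is a few per cent.

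The objection that the size is small also largely stands. A 5 to 8% shift in the ratio is about 0.2 SE. NT-proBNP is one of several secondary endpoints, and the success criterion and futility threshold rest on PVR. The interim does not change this in relative terms: at 15:5 the one-SE imbalance and the SE both grow by 0.516/0.365 = 1.41.

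Against this, the trial is run once, so the error given the observed imbalance is the relevant one, and removing it costs very little.

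**Conclusion.** The point holds as a conditional one. SAP 2.6.2 gives NT-proBNP a single baseline slope where 6MWD has one per visit, with no reason stated. If the slopes differ, the Week 25 contrast depends on the chance baseline imbalance: about 0.2 SE at a one-SE imbalance in the moderate settings, about 0.4 SE in the extreme one, and zero if the slopes are equal.

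These sizes rest on assumed correlations, log SD, residual correlation and covariance structure, none of which the documents supply. The figures do not support reading this as an invalid test or a biased analysis, since unconditional bias, coverage and type I error are essentially intact. It is a low-cost improvement to a secondary analysis and does not affect the primary PVR result.

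**What to change.** In SAP 2.6.2, specify the NT-proBNP model with treatment, visit, treatment-by-visit and baseline-by-visit, as for 6MWD. State that baseline is on the same scale as the response, so log baseline if the response is logged. If the sponsor prefers the common slope, give the reason in one sentence.

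The change is one model term. It costs one degree of freedom and, if the slopes are in fact equal, about 0.5% in variance. It needs no new data and should be made before unblinded data are seen.
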